## Magnetic Resonance Imaging (MRI)

MRI imaging is among the least invasive of all imaging modalities. The U.S. Food and Drug Administration has labeled MR systems of up to 4.0 Tesla as having "non-significant risk" and currently there is no evidence that MR imaging causes any long-term or irreversible effects in human beings. However, there are certain risks, which are detailed below.

MRI imaging utilizes magnetic fields and radiofrequency fields, both of which can be harmful in certain situations. Magnetic fields can cause ferromagnetic implants or ferromagnetic foreign bodies, such as intracranial aneurysm clips, shrapnel, and intraocular metal chips to become dislodged and tear the surrounding soft tissue. Therefore, MRI imaging is contraindicated in persons with ferromagnetic implants or ferromagnetic foreign bodies. It is also contraindicated in persons with electrically, magnetically or mechanically activated implants because the magnetic field can cause these to function erratically. In addition, persons wearing metallic objects may be at danger for them becoming dangerous projectiles, due to them inadvertently becoming introduced into the magnetic field. All subjects will be prescreened carefully and all scanners are used in accordance with guidelines set by the Bureau of Radiological Health.

#### F18-PSMA

The recommended dose is 333 MBq (9 mCi) administered as an intravenous bolus injection. The (radiation absorbed) effective dose resulting from this dose of F18-PSMA is 8 mSv. The clinical trial database for F18-PSMA includes data from 208 subjects. The mean administered activity was 333 MBq. Adverse reactions were reported in ≤1% of subjects during clinical studies with F18-PSMA. The most common adverse reactions were injection site pain, injection site erythema and dysgeusia.

**Hypersensitivity to Medications** - Occasionally, people have allergic reactions when taking any medication. Subjects may receive medications such as contrast. Hypersensitivity reactions may include symptoms such as shortness of breath, wheezing, flushing, nasal congestion and skin rash. In most cases, initial symptoms occur within minutes of drug administration and quickly reverse themselves or resolve with prompt medical treatment.

In general, allergic reactions to medicines are more likely to occur in people who have allergies to other drugs, foods, or things in the environment. Subjects will be asked about any pre-existing allergies before administering any medications during the study.

# **Incidental Findings**

Only noted clinically significant incidental findings will be communicated to the subject, per CSMC IRB and Legal Department approved policy, as a result of agreeing to undergo a research MRI scan. No reports or images will be provided to subjects and their medical records. However, MRI mapping results will be provided to the treating physicians who will use this information for MR/ultrasound guided prostate biopsy.

# 5.0 ADVERSE EVENTS (AE)

#### 5.1 Definitions

- **5.1.1** Adverse Event: An adverse event is any untoward medical occurrence in a patient receiving study intervention and which does not necessarily have a causal relationship with this intervention. An AE can therefore be any unfavorable and unintended sign (including an abnormal laboratory finding), symptom, or disease temporally associated with the use of an experimental intervention, whether or not related to the intervention.
- **5.1.2** Serious Adverse Events (SAE): A "serious" adverse event is defined in regulatory terminology as any untoward medical occurrence that:
  - Results in death. If death results from (progression of) the disease, the disease should be reported as event (SAE) itself.
  - Is life-threatening.

(the patient was at risk of death at the time of the event; it does not refer to an event that hypothetically might have caused death if it were more severe).

- Requires in-patient hospitalization or prolongation of existing hospitalization for ≥ 24 hours.
- Results in persistent or significant disability or incapacity
- Is a congenital anomaly/birth defect
- Is an important medical event

Any event that does not meet the above criteria, but that in the judgment of the investigator jeopardizes the patient, may be considered for reporting as a serious adverse event. The event may require medical or surgical intervention to prevent one of the outcomes listed in the definition of "Serious Adverse Event".

## **Evaluable for toxicity**

Any patient who receives at least one dose of investigational product is evaluable for toxicity and will be included in the safety analysis.

# Severity of Adverse Events

- Mild (grade 1): the event causes discomfort without disruption of normal daily activities.
- Moderate (grade 2): the event causes discomfort that affects normal daily activities.
- Severe (grade 3): the event makes the patient unable to perform normal daily activities or significantly affects his/her clinical status.
- Life-threatening (grade 4): the patient was at risk of death at the time of the event.
- Fatal (grade 5): the event caused death.

#### Reporting Requirements for Adverse Events

Step 1: Identify the type of adverse event using the NCI Common Terminology Criteria for Adverse Events (CTCAE – CURRENT VERSION 5.0).

Step 2: Grade the adverse event using the CTCAE – CURRENT VERSION 5.0.

Step 3: Determine whether the adverse event is related to the protocol therapy

#### Attribution categories are as follows:

- Definite The AE is clearly related to the study treatment.
- Probable The AE is likely related to the study treatment.
- Possible The AE may be related to the study treatment.
- Unlikely The AE is doubtfully related to the study treatment.
- Unrelated The AE is clearly NOT related to the study treatment.

Note: This includes all events that occur within 30 days of the last dose of protocol treatment. Any event that occurs more than 30 days after the last dose of treatment and is attributed (possibly, probably, or definitely) to the agent(s) must also be reported accordingly.

Step 4: Determine the prior experience of the adverse event.

Expected events are those that have been previously identified as resulting from administration of the agent. An adverse event is considered unexpected, for expedited reporting purposes only, when either the type of event or the severity of the event is not listed in:

- the current known adverse events listed in the Agent Information Section of this protocol;
- the drug package insert
- the current Investigator's Brochure

### **5.1.3** Unanticipated Problem (UP)

Unanticipated problems include any incident, experience, or outcome that meets all of the following criteria:

- Unexpected (in terms of nature, severity, frequency) given (a) the
  research procedures that are described in the protocol-related
  documents, such as the IRB-approved research protocol and informed
  consent document; and (b) the characteristics of the subject population
  being studied;
- Related or possibly related to participation in the research (possibly related means there is a reasonable possibility that the incident, experience, or outcome may have been caused by the procedures involved in the research); and
- Suggests that the research places subjects or others at a greater risk of harm (including physical, psychological, economic, or social harm) than was previously known to an individual or group of individuals (including research subjects, research staff, or others not directly involved in the research).

# 5.2 Reporting Requirements

#### 5.2.1 Reporting to Principal Investigator

The Principal Investigator must be notified by study staff or co-investigators within 24 hours of learning of any serious adverse events, regardless of attribution, occurring during the study or within 30 days (refer to Section 7.1) of the last administration of the study drug.

Phone Number for Expedited Reporting:
[name]
[contact]
Alternate Phone Number for Expedited Reporting:
ALTERNATE NAME AND PHONE
[name]
[contact]

# 5.2.1.1 Participating Site Reporting Responsibilities

Any serious adverse event or unanticipated problem at all participating sites, which occur in research subjects on protocols for which SOCCI is the DSMC of record requires reporting to the DSMC regardless of whether IRB reporting is required. All SAEs/UPIRSOs occurring during the protocol-specified monitoring period should be submitted to the SOCCI DSMC, copying the CCTO Coordinating Center Study Lead, as detailed in section 7.4.2.3. In addition, for participating centers other than SOCCI, local IRB guidance should be followed for local reporting of serious adverse events.

If the event occurs on a multi-site clinical trial coordinated by the SOCCI, the Study Lead at the Coordinating Center will ensure that all participating sites are notified of the event and resulting action, according to FDA guidance for expedited reporting. Copies of all serious adverse event reports or unanticipated problems reports will be kept on file in the Cedars-Sinai CCTO.

Reporting of SAEs/UPIRSOs must be accompanied by a cover letter which: identifies the event, is signed by the local principal investigator or treating physician from the participating site, includes the applicable study number and title, and contains the following:

- Site assessment of the event attribution to investigational product or study procedure
- Site assessment of event expectedness (expected vs. unexpected)
- Assessment of whether or not the research places subjects at a greater risk of harm than was previously known or recognized
- Assessment of the event's effect on the risk to benefit ratio
- Statement as to whether the informed consent statement should reflect changes in the potential risks involved
- Statement as to whether the event has been reported previously, and if so, whether the frequency is considered unusually high

Send to: SOCCI Cancer Clinical Trials Office

ATTN: SPIN/ Protocol # STUDY00000832

[contact]

E-mail: [contact]

CC: [contact]

# 5.2.1.2 Reporting to DSMC:

Serious Adverse Events deemed to be related to the protocol and on-study deaths, including death of a research subject unless the death is expected (e.g. due to disease progression) to be reported to the DSMC within 24 hours of awareness. Hardcopies or electronic versions of the MedWatch Form 3500A (Mandatory Reporting) or SAE Form, along with any other supporting documentation available, should be submitted to the DSMC Coordinator. The DSMC Coordinator will forward the information to the DSMC Chair, and/or medical monitor. The DSMC Chair will review all SAEs/UPIRSOs upon receipt from the DSMC Coordinator and determination of whether the following actions are required: 1) takes action immediately, 2) convenes a special DSMC session (physical or electronic), or 3) defers the action until a regularly scheduled DSMC meeting. Reports are to be emailed to the DSMC team at [contact].

IIT2020-14-[name]-HIFU Version 8.0: 08 November 2023

# **5.2.1.3** Reporting to Drug Manufacturer

In accordance with Applicable Laws, Study Staff will advise the sponsor of any adverse reactions or side effects occurring during and after the conduct of the Study that become known to it. Institution agrees and shall cause Principal Investigator to comply with all applicable safety reporting regulations as set forth in the Code of Federal Regulations. Any correspondence to the FDA regarding adverse events or other safety issues associated with the Study Drug will be simultaneously copied via facsimile or e-mail to Progenics. Within 24 hours of becoming aware of a serious adverse event, Institution will communicate the occurrence of such event to Progenics and, if another drug or product is being used in the Study, to the manufacturer of the associated drug or product. Please note that the reporting period begins when a subject receives the Study Drug. Adverse event reports should reference the Progenics Clinical Grant Number, which will be supplied to the Principal Investigator by Progenics. The MedWatch 3500A form or such other form as may be required by the FDA from time to time should be utilized to report serious adverse events to the FDA. For Progenics products, report the adverse event information to the following: DocuSign Envelope ID: 3191B4AA-7E39-4BB7-9A69-037F85430112 DocuSign Envelope ID: C3AF2C8C-BFA9-423E-95B8-26A66809B56A4 Pharmacovigilance Agent [contact] or [name] [contact] Email: [contact]

# 5.2.2 Reporting to the Institutional Review Board (IRB)

The IRB must be notified within 10 business days of "any unanticipated problems involving risk to subjects or others."

- 1. Any serious event (injuries, side effects, deaths or other problems), which in the opinion of the Principal Investigator was unanticipated, involved risk to subjects or others, and was possibly related to the research procedures.
- 2. Any serious accidental or unintentional change to the IRB-approved protocol that alters the level of risk.
- 3. Any deviation from the protocol taken without prior IRB review to eliminate apparent immediate hazard to a research subject.
- 4. Any new information (e.g., publication, safety monitoring report, updated sponsor safety report), interim result or other finding that indicates an unexpected change to the risk/benefit ratio for the research.
- 5. Any breach in confidentiality that may involve risk to the subject or others.
- 6. Any complaint of a subject that indicates an unanticipated risk or that cannot be resolved by the Principal Investigator.

### 5.2.3 Reporting to the FDA

The sponsor-investigator of the IND, or designee at the Coordinating Center, must submit all reported SAEs from all participating sites to the FDA on the FDA Form 3500A (MedWatch) according to the following reporting criteria:

## 7-Day Reports:

The investigator-sponsor of the IND must notify the FDA as soon as possible but no later than **7 calendar** days after the investigator-sponsor's initial receipt of the

information and all participating sites in a written IND safety report of any adverse reaction:

- fatal or life-threatening adverse reaction that is both
- suspected to be associated with use of the drug and
- unexpected

# 15-Day IND Reports:

The investigator-sponsor of the IND must notify the FDA as soon as possible but no later than **7 calendar** days after the investigator-sponsor's initial receipt of the information and all participating sites in a written IND safety report of any adverse reaction:

- suspected to be associated with use of the drug that is both
- serious and
- unexpected

Copies of Expedited Safety Reports will be kept in the Trial Master File in the SOCCI CCTO.

#### 6.0 STATISTICAL ANALYSIS

# 6.1 HIFU Phase II Study

Our preliminary data suggests that up to 60% of tumors invisible to standard mpMRI are detected on hrMRI in an active surveillance population. It is unclear how many additional lesions will be identified on PSMA PET-MRI. Since all areas of concern will be biopsied and only biopsy-proven tumors will be treated with HIFU, the morbidity of the surgical intervention is minimized and its potential to achieve cure is maximized.

Power Assessment: The main hypothesis to be tested is whether the sensitivity of PSMA PET-hrMRI is greater than mpMRI alone in 20% considering the prostate divided in 6 sections for each patient. The power is evaluated using 1000 simulations based on the McNemar's type test proposed by Yang et al. (17,2010). Data is generated based on four correlations: r1: between lesions evaluated by PSMA PET-hrMRI for the same patient, r2: between lesions evaluated by mpMRI for the same patient, r3: between evaluations PSMA PET-hrMRI and mpMRI for the same lesion and r4: between evaluations PSMA PET-hrMRI and mpMRI for the different lesions at the same patient. Based on preliminary data, we estimated mpMRI sensitivity of 42%, (r1, r2, r3, r4) = (-0.249, -0.119, 0.714, -0.172) using Spearman correlation, average number of lesions of 2.5 per patient and prevalence of patients with at least one positive biopsy section equal to 82%. The results are presented in Table 1.

**Table 1.** Power for McNemar test proposed by Yang et al. (2010) to detect a difference of 20% between sensitivities of the combination (PET-hrMRI or mpMRI) and mpMRI

Total Sample # Patients with at least one positive biopsy
Size section Power

20	16	70.2
25	21	81.5
30	25	88.9
35	29	93.1
40	33	95.5

The minimum sample size to reach at least 85% of power is 30 patients with complete imaging data. Patients with incomplete imaging data will be replaced.

Statistical Analysis: Sensitivities will be compared using McNemar's type test proposed by Yang et al. (17,2010). for cluster matched binary data. In addition, the 95% confidence interval for difference between sensitivities will be calculated as proposed by Yang et al. (18,2012).

Secondary Endpoints: Negative biopsy rate within treatment zones on standard 12-core biopsy 6 months following HIFU therapy; rate of high grade cancer in the untreated lobe.

Exploratory Endpoint: Formalin-fixed paraffin embedded biopsy tissue will be requested from a subset of patients for RNAseq transcriptome analysis. The number of cases analyzed will depend on availability of future funding. The subset of cases requested will depend on the exploratory object of the pilot study and may include discovery of signatures to predict presence of high grade cancer, unilateral disease or treatment success.

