Statistical analysis	Our hypothesis is that 20% of biopsy-proven tumors will be detected on PET-hrMRI and not on standard MRI. If we assume that no biopsy proven tumors will only be detected on standard MRI, at alpha=0.05, n=40 provides a power of at least 90% when we account for 5 cases that will not be evaluable. The RP phase II study is a parallel study arm using PSMA-PET imaging for intraprostatic cancer detection, but using radical prostatectomy pathology as the gold standard. The radical prostatectomy pilot arm will allow us to compensate for limitations and describe this data in parallel with the HIFU analysis.		

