## 3.3 Study endpoints

Primary Endpoint (HIFU): Number of additional biopsy-proven cancers that novel imaging modalities of hrMRI and/or F18-PSMA PET would detect when compared to reference standard imaging of mpMRI in patients undergoing HIFU procedure.

Secondary Endpoint (HIFU): Negative biopsy rate on standard 12-core biopsy 6 months following HIFU therapy.

**Primary Endpoint (Prostatectomy):** To determine the sensitivity in detection of prostatic carcinoma of novel imaging modalities of hrMRI and/or F18-PSMA PET compared to reference standard mpMRI in patients scheduled to undergo radical prostatectomy.

Secondary Endpoint (Prostatectomy): Specificity of hrMRI, F18-PSMA PET and mpMRI for detecting all tumors and metastasis at 6 months follow up.

**Exploratory Endpoint:** RNAseq transcriptome analysis of lesions that are positive on mapping biopsy. Sensitivity and specificity of PET-hrMRI for detecting all tumors detected on prostatectomy pathology.

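### The HIFU primary endpoint counts cancers, but Section 6.1 states its hypothesis over six prostate sections, mixes sections with lesions, and gives no rule linking the units

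*Combined protocol and SAP*

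**What the plan says.** **Endpoint.** Section 3.3 gives the HIFU primary endpoint as "Number of additional biopsy-proven cancers that novel imaging modalities of hrMRI and/or F18-PSMA PET would detect" relative to mpMRI, and the objectives in the Study Summary repeat it. The Summary's statistical paragraph hypothesises that "20% of biopsy-proven tumors will be detected on PET-hrMRI and not on standard MRI". In both places the thing counted is a cancer or tumor.

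**Hypothesis.** The Power Assessment in Section 6.1 asks whether PET-hrMRI sensitivity is "greater than mpMRI alone in 20% considering the prostate divided in 6 sections for each patient". The patient column of Table 1 is also defined by a positive biopsy section.

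**Planning inputs, same paragraph.** The correlations are defined by lesion (for example "r1: between lesions evaluated by PSMA PET-hrMRI for the same patient"), and so is the "average number of lesions of 2.5 per patient". The proportion of analysable patients is defined by section: "prevalence of patients with at least one positive biopsy section equal to 82" per cent.

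**Test.** The Statistical Analysis paragraph of Section 6.1 names a clustered McNemar-type test of sensitivities and does not name the unit.

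**Section 6.2.** The prostatectomy cohort is to be analysed per lesion. It expects six lesions per patient on average and for that reason reuses the HIFU Table 1.

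**What is absent.** The imaging protocol outlines each suspicious lesion slice by slice, and the mapping biopsy combines a sextant template with targeted cores. Nothing says how an outline or a core is assigned to a section, how a cancer crossing a boundary is counted, or how section results become a number of cancers.

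**The concern.** Sections and cancers are different units. One cancer in two sextants is two sections; two cancers in one sextant are one section. A test over sections therefore does not measure the quantity in Section 3.3 unless a rule connects them, and none is given.

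This matters because the sensitivity comparison is the only primary analysis planned for this cohort, so its result is what will stand behind any statement about additional cancers. The protocol already moves between the units. Section 2.5 reports the preliminary study in zones (22 of 23 against 14 of 23) and then summarises it in tumors, and Section 6.1 carries the tumor wording forward. The rationale in Section 2.8 rests on finding a separate missed focus, such as one in the opposite lobe. Marking more of a cancer that mpMRI already showed is a different result. If the unit is chosen after the data are seen, the primary conclusion could depend on that choice.

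**Working it through.** **1. Inputs (Section 6.1).** mpMRI sensitivity 0.42 and a 20-point difference, so 0.62 against 0.42 (read as absolute); 2.5 units per patient; 82% of patients analysable; four correlations. The plan states: "we estimated mpMRI sensitivity of 42%, (r1, r2, r3, r4) = (-0.249, -0.119, 0.714, -0.172) using Spearman correlation". At 30 patients, 0.82 × 30 = 24.6, shown as 25 in Table 1, with stated power 88.9%.

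**2. Reproducing Table 1.** For patient k with m_k units, let S_k be the sum over units of (PET-hrMRI result − mpMRI result). The statistic is T = (ΣS_k)² / V. The centred variance is V = [K/(K−1)] Σ(S_k − m_k·d)², where d = ΣS_k/Σm_k; the uncentred variance is V = ΣS_k². Reject in favour of PET-hrMRI if T > 3.84 and ΣS_k > 0 (two-sided 0.05; the plan does not state sidedness). I used 20,000 simulated trials, with 2 or 3 units per positive patient in equal shares.

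| Patients (positive) | Stated | Centred | Uncentred |
|---|---|---|---|
| 20 (16) | 70.2 | 72.4 | 63.5 |
| 25 (21) | 81.5 | 83.6 | 78.8 |
| 30 (25) | 88.9 | 89.0 | 86.5 |
| 35 (29) | 93.1 | 93.1 | 91.7 |
| 40 (33) | 95.5 | 95.6 | 94.8 |

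Two assumptions are mine. First, the correlations are applied to latent normal variables. As a plain binary correlation, 0.714 is not attainable with these sensitivities: the maximum is (0.42 − 0.62×0.42)/√(0.62×0.38×0.42×0.58) = 0.1596/0.2396 = 0.666. Second, 0.62 is taken as the marginal sensitivity of the novel reading. The agreement does not identify the unit, because the calculation is the same whether the 2.5 are sections or lesions.

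**3. Size of a 20-point difference in sections.**
- 2.5 per positive patient: 25 × 2.5 = 62.5 sections; 0.20 × 62.5 = 12.5.
- 2.5 averaged over all 30 patients: 30 × 2.5 = 75 sections; 0.20 × 75 = 15.

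So 12.5 net extensions of already-seen cancers into neighbouring biopsy-positive sextants equal 12.5/62.5 = 20 points, or 12.5/75 = 16.7 points. Only sections that are biopsy-positive and unmarked by mpMRI can contribute, since biopsy-negative sections do not enter sensitivity.

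**4. What the section test does with such a gain.** Suppose both methods see exactly the same cancers. Each positive section is discordant by chance with probability 0.047 in each direction (assumed), and any net gain comes only from wider outlining into positive sections. With 25 positive patients and the centred variance:

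| Net section gain (points) | Significant for PET-hrMRI |
|---|---|
| 0 | 3% |
| 5 | 20% |
| 10 | 48% |
| 15 | 73% |
| 20 | 89% |

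The number of additional cancers is zero in every row. The test responds to a section gain whatever its source.

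**5. Power if the unit is the cancer.** Assume that each cancer spans s of the 2.5 positive sextants, giving 2.5/s cancers per positive patient, with 25 positive patients and the other inputs unchanged:

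| s | Cancers per patient | Centred | Uncentred |
|---|---|---|---|
| 1 | 2.5 | 88.9% | 86.4% |
| 1.25 | 2.0 | 81.9% | 77.1% |
| 1.5 | 1.67 | 74.6% | 68.0% |
| 2 | 1.25 | 62.8% | 54.4% |
| 2.5 | 1.0 | 55.7% | 46.4% |

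Of the spans tried, only s = 1 reaches the 85% target, that is, only if the 2.5 units are already distinct cancers.

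**The case against.** Four points can be made for the plan.

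First, a reader might infer that the test has been shown to count sextants. The documents do not go that far. The six-section phrase appears only under Power Assessment, the paragraph specifying the test names no unit, and the correlations and the 2.5 average are given by lesion. This stands: the defect is a mixed and undefined unit, with the section reading the more natural one.

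Second, a reader might infer that any larger outline of a known cancer helps PET-hrMRI. It does not. The neighbouring sextant must itself be biopsy-positive and unmarked by mpMRI, in which case mpMRI did miss proven tumor there. For mapping a focal treatment that is useful information. This also stands, and it is a reason to keep a section-level analysis. It does not turn the result into a count of additional cancers.

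Third, the test compares sensitivities and does not label a discordant section a new cancer, and the outlines and targeted biopsies would allow a separate count. That is correct, but the plan does not say how such a count would be made, and no other primary analysis is specified.

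Fourth, the 12.5-section example is chosen to equal 20 points, assumes net movement in one direction, and gives only 16.7 points on 75 sections. It is an illustration and not a forecast. The opposite error, two cancers in one sextant counted once, could hide a newly found cancer and is not quantified here.

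**Conclusion.** The inconsistency is on the page and should be fixed. Section 3.3 and the Summary promise a number of cancers, Section 6.1 states its hypothesis over sections, the planning inputs use both words, and no rule connects them. If the plan is followed on its most natural reading, a section-level test with 88.9% stated power would be the only inferential support for a claim about cancers.

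The size depends on how many sextants a cancer occupies, which the documents do not give. Under the assumptions shown, a net section gain of 10 to 20 points arising wholly from wider outlining of shared cancers would be significant in 48% to 89% of trials. Power for the cancer as the unit ranges from 88.9% at one sextant per cancer to 62.8% at two (centred variance).

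The documents do not support saying that a positive result would be an artefact of outlining, or that a 20-point gain without new cancers is to be expected.

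**What to change.** Use one unit in Section 3.3, the Study Summary, Section 6.1 and Table 1.

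**Cheapest version: keep the six-section test.** Restate the primary endpoint as the difference in section-level sensitivity, that is, additional biopsy-positive sections detected. Label the 2.5 average and Table 1 as section-level, if that is what they are, and add a sentence on how outlines and targeted cores are assigned to sections. Report the number of additional cancers separately and descriptively, and do not present the section test as evidence for it. The cost is wording only; no new procedures or data are needed.

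**Alternative: make the cancer the unit.** Prespecify a rule for deciding when positive sections belong to the same cancer and how boundary-crossing cancers are counted. The rule should not let the outline from the modality under test define the unit on its own: one large PET-hrMRI outline could merge two separate foci, and mpMRI would then be credited with both after marking one. Restate the 2.5 average, the sensitivity, the correlations and the Table 1 power for that unit. This costs new planning inputs as well as a rerun of the simulation. Power at 25 positive patients may fall below 88.9%, to about 75% at 1.5 sextants per cancer and 63% at 2 (both spans assumed). The six-section comparison can then stay as a supportive analysis of extent.
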